14.5 Disclosure and Publication Policy

All information provided regarding the study, as well as all information collected/documentated during the course of the study, will be regarded as confidential. SCRI Innovations reserves the right to release literature publications based on the results of the study. Results from the study will be published/presented as per SCRI Innovations publication process.

Inclusion of the investigator in the authorship of any multicenter publication will be based upon substantial contribution to the design, analysis, interpretation of data, drafting and/or critically revising any manuscript(s) derived from the study. The investigator acknowledges that the study is part of a multicenter study and agrees that any publication by the investigator of the results of the study conducted at research site shall not be made before the first multicenter publication. In the event there is no multicenter publication within fifteen (15) months after the study has been completed or terminated at all study sites, and all data has been received, the investigator shall have the right to publish its results from the study, subject to the notice requirements described herein and subject to acknowledgement of the funding partner as appropriate. Investigator shall provide the funding partner thirty (30) days to review a manuscript, and 1 week (7 days) to review any poster presentation, abstract or other written or oral material which describes the results of the study for the purpose only of determining if any confidential or patentable information is disclosed thereby. If the funding partner requests in writing, the investigator shall withhold any publication or presentation an additional sixty (60) days solely to permit the

CONFIDENTIAL

STUDY DRUG(S): EVEROLIMUS
FINAL PROTOCOL DATE: 19 JUNE 2014

SCRI INNOVATIONS STUDY NUMBER: BRE 212
VERSION 1.0

funding partner to seek patent protection and to remove any funding partner Confidential Information from all publications.

CONFIDENTIAL

STUDY DRUG(S): EVEROLIMUS
FINAL PROTOCOL DATE: 19 JUNE 2014

SCRI INNOVATIONS STUDY NUMBER: BRE 212
VERSION 1.0

16. APPENDICES

Appendix A: ECOG Performance Status Criteria

ECOG Performance Status Scale		Karnofsky Performance Scale	
Grade	Descriptions	Percent	Description
0	Normal activity. Fully active, able to carry on all pre-disease performance without restriction.	100	Normal, no complaints, no evidence of disease.
		90	Able to carry on normal activity; minor signs or symptoms of disease.
1	Symptoms, but ambulatory. Restricted in physically strenuous activity, but ambulatory and able to carry out work of a light or sedentary nature (e.g., light housework, office work).	80	Normal activity with effort; some signs or symptoms of disease.
		70	Cares for self, unable to carry on normal activity or to do active work.
2	In bed <50% of the time. Ambulatory and capable of all self-care, but unable to carry out any work activities. Up and about more than 50% of waking hours.	60	Requires occasional assistance, but is able to care for most of his/her needs.
		50	Requires considerable assistance and frequent medical care.
3	In bed > 50% of the time. Capable of only limited self-care, confined to bed or chair more than 50% of waking hours.	40	Disabled, requires special care and assistance
		30	Severely disabled, hospitalization indicated. Death no imminent.
4	100% bedridden. Completely disabled. Cannot carry on any self-care. Totally confined to bed or chair.	20	Very sick, hospitalization indicated. Death not imminent.
		10	Moribund, fatal processes progressing rapidly.
5	Dead	0	Dead

CONFIDENTIAL

STUDY DRUG(S): EVEROLIMUS
FINAL PROTOCOL DATE: 19 JUNE 2014

SCRI INNOVATIONS STUDY NUMBER: BRE 212
VERSION 1.0

Appendix B: New York Heart Association (NYHA) Classification of Cardiac Disease

The following table presents the NYHA classification of cardiac disease.

Class	Functional Capacity	Objective Assessment
I	Patients with cardiac disease but without resulting limitations of physical activity. Ordinary physical activity does not cause undue fatigue, palpitation, dyspnea, or anginal pain.	No objective evidence of cardiovascular disease.
II	Patients with cardiac disease resulting in slight limitation of physical activity. They are comfortable at rest. Ordinary physical activity results in fatigue, palpitation, dyspnea, or anginal pain.	Objective evidence of minimal cardiovascular disease.
III	Patients with cardiac disease resulting in marked limitation of physical activity. They are comfortable at rest. Less than ordinary activity causes fatigue, palpitation, dyspnea, or anginal pain.	Objective evidence of moderately severe cardiovascular disease.
IV	Patients with cardiac disease resulting in inability to carry on any physical activity without discomfort. Symptoms of heart failure or the anginal syndrome may be present even at rest. If any physical activity is undertaken, discomfort is increased.	Objective evidence of severe cardiovascular disease.

Source: The Criteria Committee of New York Heart Association. Nomenclature and Criteria for Diagnosis of Diseases of the Heart and Great Vessels. 9th Ed. Boston, MA: Little, Brown & Co; 1994:253-256.

CONFIDENTIAL

STUDY DRUG(S): EVEROLIMUS
FINAL PROTOCOL DATE: 19 JUNE 2014

SCRI INNOVATIONS STUDY NUMBER: BRE 212
VERSION 1.0

Appendix C: Guidelines for Female Patients of Childbearing Potential and Fertile Male Patients

Acceptable Contraception Methods:

Women of childbearing potential, defined as all women physiologically capable of becoming pregnant, must use highly effective contraception during the study and for 8 weeks after stopping treatment.

Highly effective contraception is defined as either:

True Abstinence When this is in line with the preferred and usual lifestyle of the subject. Periodic abstinence (e.g., calendar, ovulation, symptothermal, post-ovulation methods) and withdrawal are not acceptable methods of contraception.

Sterilization When a woman of childbearing potential has had surgical bilateral oophorectomy (with or without hysterectomy) or tubal ligation at least six weeks prior to study entry. In case of oophorectomy alone, only when the reproductive status of the woman has been confirmed by follow up hormone level assessment.

Male Partner Sterilization When the appropriate post-vasectomy documentation of the absence of sperm in the ejaculate.

Use of a combination of any two of the following (one from a + one from b):

- a) Placement of an intrauterine device (IUD) or intrauterine system (IUS).
- b) Barrier methods of contraception: Condom or Occlusive cap (diaphragm or cervical/vault caps) with spermicidal foam/gel/film/cream/vaginal suppository.

Fertile male patients, defined as all males physiologically capable of conceiving offspring, with female partners of child-bearing potential must use condoms plus spermicidal agent during the study treatment period and for 8 weeks after the last dose of study drug, and should not father a child during this period.

Male patients must also refrain from donating sperm during their participation in the study.

The following are acceptable forms of barrier contraception:

- Latex condom, diaphragm or cervical/vault cap when used with spermicidal foam/gel/film/cream/suppository

Unacceptable Contraception Methods: for women of childbearing potential include:

- IUD progesterone T
- Female condom

CONFIDENTIAL

STUDY DRUG(S): EVEROLIMUS
FINAL PROTOCOL DATE: 19 JUNE 2014

SCRI INNOVATIONS STUDY NUMBER: BRE 212
VERSION 1.0

- Natural family planning (rhythm method) or breastfeeding
- Fertility awareness
- Withdrawal
- Cervical shield

Pregnancies

To ensure subject safety, each pregnancy in a subject on study treatment must be reported to the SCRI Innovations Safety Department within 24 hours of learning of its occurrence. The pregnancy should be followed up for 3 months after the termination of the pregnancy to determine outcome, including spontaneous or voluntary termination, details of the birth, and the presence or absence of any birth defects, congenital abnormalities, or maternal and/or newborn complications.

Pregnancy should be recorded on a Clinical Study Pregnancy Form and reported by the investigator to **SCRI Innovations Safety Department**. Pregnancy follow-up should be recorded on the same form and should include an assessment of the possible relationship to the study drug of any pregnancy outcome. Any SAE experienced during pregnancy must be reported on the SAE Report Form.

Pregnancy outcomes must be collected for the female partners of any males who took study treatment in this study. Consent to report information regarding these pregnancy outcomes should be obtained from the mother.

Women Not of Childbearing Potential are defined as Follows:

- Women are considered post-menopausal and not of childbearing potential if they have had 12 months of natural (spontaneous) amenorrhea with an appropriate clinical profile (e.g., age appropriate, history of vasomotor symptoms).
- Women who are permanently sterilized (e.g., tubal occlusion, hysterectomy, bilateral salpingectomy, bilateral oophorectomy).
- Women who are >45 years-of-age, not using hormone-replacement therapy and who have experienced total cessation of menses for at least 12 months OR who have a follicle stimulating hormone (FSH) value >40 mIU/mL and an estradiol value <40 pg/mL (140 pmol/L).
- Women who are >45 years-of-age, using hormone-replacement therapy and who have experienced total cessation of menses for at least 1 year OR who have had documented evidence of menopause based on FSH >40 mIU/mL and estradiol <40 pg/mL prior to initiation of hormone-replacement therapy.

CONFIDENTIAL

STUDY DRUG(S): EVEROLIMUS
FINAL PROTOCOL DATE: 19 JUNE 2014

SCRI INNOVATIONS STUDY NUMBER: BRE 212
VERSION 1.0

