3. STUDY PATIENT POPULATION AND DISCONTINUATION

3.1 Inclusion Criteria

Patients must meet all of the following criteria in order to be included in the research study:

1. Histologic diagnosis of unresectable, locally recurrent or MBC.
2. ER and/or PR-positive tumors with staining by immunohistochemistry (IHC) based on the most recent biopsy.
3. Only 1 previous chemotherapy regimen for MBC. Patients progressing while receiving adjuvant endocrine therapy or progressing <12 months from completion of adjuvant endocrine therapy are eligible.

CONFIDENTIAL

STUDY DRUG(S): EVEROLIMUS
FINAL PROTOCOL DATE: 19 JUNE 2014

SCRI INNOVATIONS STUDY NUMBER: BRE 212
VERSION 1.0

4. Progressed on anti-estrogen therapy (tamoxifen, fulvestrant, anastrozole, letrozole, exemestane, toremifene, or LHRH agonists in conjunction with anti-estrogen therapy) defined as:

- Recurrence while on, or within 12 months of end of anti-estrogen therapy for early stage breast cancer, or
- Progression while on, or within one month of anti-estrogen therapy for locally advanced or metastatic breast cancer.

Note: No washout for anti-estrogen therapy required.

Anti-estrogen therapy does not have to be the last treatment prior to study entry.

5. Post- menopausal or pre/peri-menopausal women on tamoxifen. LHRH agonists may be used to render ovarian suppression with postmenopausal ranges of estradiol or FSH per institutional guidelines.

6. HER2-negative breast cancer, defined as follows:

- Fluorescent In Situ Hybridization (FISH)-negative (FISH ratio <2.0), or
- IHC 0-1+, or
- IHC 2-3+ AND FISH-negative (FISH ratio <2.0).

7. Measureable disease as measured by Response Evaluation Criteria in Solid Tumors (RECIST) criteria version 1.1 (See Appendix E) or evaluable bone lesions, lytic or mixed, in absence of measureable disease by RECIST criteria.

8. Adequate hematologic function, defined by:

- Absolute neutrophil count (ANC) $\geq 1.5 \times 10^9/L$
- Platelet count $\geq 100 \times 10^9/L$
- Hemoglobin $>9 \text{ g/dL}$.

9. Adequate liver function, defined by:

- Aspartate aminotransferase (AST) and alanine aminotransferase (ALT) $\leq 2.5 \times$ the upper limit of normal (ULN) or $\leq 5 \times$ ULN in presence of liver metastases)
- Total bilirubin $\leq 1.5 \times$ ULN.

10. Adequate renal function, defined by:

- Serum creatinine $\leq 1.5 \times$ ULN or calculated creatinine clearance of $\geq 40 \text{ ml/min}$.

CONFIDENTIAL

STUDY DRUG(S): EVEROLIMUS

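### Appendix C's cessation-of-menses criteria for women over 45 do not require a natural cause, so drug-induced amenorrhea can count as absence of childbearing potential

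*Protocol*

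**What the plan says.** Appendix C of the protocol defines women of childbearing potential broadly, "defined as all women physiologically capable of becoming pregnant", and says that they "must use highly effective contraception during the study and for 8 weeks after stopping treatment". It then lists women who are not of childbearing potential, in four bullets:

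- **Bullet 1:** "Women are considered post-menopausal and not of childbearing potential if they have had 12 months of natural (spontaneous) amenorrhea with an appropriate clinical profile".
- **Bullet 2:** women who are permanently sterilized.
- **Bullet 3:** women over 45, "not using hormone-replacement therapy and who have experienced total cessation of menses for at least 12 months", or who meet an FSH and estradiol threshold.
- **Bullet 4:** women over 45 "using hormone-replacement therapy and who have experienced total cessation of menses for at least 1 year", or with hormone evidence of menopause from before the replacement therapy began.

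Section 3.1 (criterion 5) admits pre/peri-menopausal women on tamoxifen and adds that "LHRH agonists may be used to render ovarian suppression with postmenopausal ranges of estradiol or FSH per institutional guidelines". Criterion 3 covers prior chemotherapy, and criterion 4 requires that every patient has progressed on anti-estrogen therapy.

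**The concern.** Bullet 1 makes the cause of amenorrhea decisive. The menses limbs of bullets 3 and 4 do not mention it. In this trial that matters more than usual, because the study and prior treatments include drugs that can stop menstruation. Absence of periods on such a drug does not by itself show that a woman cannot conceive. That is a clinical judgement, but the protocol makes it too: bullet 1 insists on a natural cause, and Appendix D (footnote h) requires pregnancy tests in pre/peri-menopausal women whether or not their ovaries are suppressed.

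At stake is a safety rule. Appendix C's stricter contraception standard depends on the childbearing-potential label, and so does the duty in Section 3.4 to contact the investigator about a suspected pregnancy. The statistical design is not involved.

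**Working it through.** The plan states no figure on this point, so the check is mainly a comparison of texts.

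**1. Are the bullets alternatives?** Yes. Bullet 3 is for women not using hormone replacement and bullet 4 for women using it. No woman can meet both at once, so each bullet must be sufficient alone.

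**2. Test case.** Take a woman over 45, not on hormone replacement, not sterilized, with at least 12 months of amenorrhea on an LHRH agonist.

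| Text | Result |
|---|---|
| Bullet 1 | Not met: the amenorrhea is not natural |
| Bullet 2 | Not met |
| Bullet 3, menses limb | Met: age, no hormone replacement, 12 months |
| Appendix C definition of childbearing potential | May be met: she may be physiologically able to conceive |
| Appendix D, footnote h | If pre/peri-menopausal, tested at baseline and every 2 cycles (8 weeks) |

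The protocol can thus test her for pregnancy every 8 weeks while bullet 3 lists her as not of childbearing potential. Chemotherapy or an anti-estrogen as the cause of the amenorrhea gives the same result under bullets 1 and 3.

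**3. Can she enrol?** Yes, under criteria 3 to 5 of Section 3.1. Bullet 4 has the same gap, but few patients with hormone receptor-positive cancer would be expected to use hormone replacement (a judgement; the documents give no count).

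**4. What does the label change for her?**

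- *Contraception standard.* Section 3.4 requires barrier contraception or abstinence of every patient. Appendix C's stricter standard accepts true abstinence, sterilization of the woman or her partner, or an intrauterine device or system combined with a barrier method. For a woman who relies on a barrier method, the difference is the added device.
- *Duty to contact the investigator.* She falls outside it formally. The one sign that Section 3.4 names is a missed or late period, which a woman without periods for a year cannot notice, so little is lost.

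**5. For how long?** One month is 30.4375 / 7 = 4.348 weeks. The stricter standard covers treatment plus 8 weeks. If treatment ends at progression (assumption), at the anticipated median PFS of 5 months in Section 10.2, that is 5 x 4.348 + 8 = 29.7 weeks. Section 3.4's universal rule runs for 6 months after the last dose, or 6 x 4.348 = 26.1 weeks. For the last 26.1 - 8 = 18.1 weeks of it, the two groups follow the same rule. These figures measure how long a rule applies, not a risk of pregnancy.

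**The case against.** The strongest reply is that the exposure is already covered:

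- Section 3.4 binds all patients, including those already sterilized, to barrier contraception or abstinence, and for longer after treatment than Appendix C does.
- Pregnancy testing follows pre/peri-menopausal status, not the childbearing-potential label.
- Pregnant women are excluded.
- Section 3.4 withholds drug from any patient whom the investigator suspects of being pregnant.
- Appendix C says that "each pregnancy in a subject on study treatment must be reported".
- A careful investigator could apply the broad definition in Appendix C and disregard bullet 3.

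All of this stands, and it is why the point is minor. It does not make bullet 3 agree with bullet 1, and it leaves about 9 sites to settle the conflict separately.

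A second reply is that the FSH and estradiol limbs are silent on cause too. That is true, but those limbs rest on measured hormone values and do not infer menopause from absent periods. The point does not extend to them.

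A reader might infer more than the documents support:

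- *That such a woman escapes pregnancy testing.* Sections 7.1 to 7.3 and Appendix D test all pre/peri-menopausal women, suppressed or not, and bullet 3 does not call her post-menopausal. Testing would lapse only if a site used bullet 3 to decide menopausal status, which the protocol does not tell it to do.
- *That she is left without a contraception requirement.* Section 3.4 still applies to her in full.
- *That many women are affected.* The documents give no count.

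**Conclusion.** The inconsistency is real. In bullets 3 and 4 of Appendix C, a woman over 45 with at least 12 months of drug-induced amenorrhea can be listed as not of childbearing potential although she may meet the appendix's own definition of it. The practical loss is the stricter contraception standard during treatment and for 8 weeks after, and it falls mainly on women who rely on a barrier method.

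The size is small, and the number of women affected cannot be estimated from the documents. The conclusion rests on reading the bullets as alternatives, which their content requires, and on the clinical judgement that induced amenorrhea does not by itself exclude pregnancy. No endpoint, analysis population or sample-size element depends on it. It is worth correcting because the text is an operative safety rule and the correction is short.

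**What to change.** In the menses limbs of bullets 3 and 4, replace 'total cessation of menses' with 'natural (spontaneous) total cessation of menses'. Leave bullets 1 and 2, the FSH and estradiol limbs, Section 3.4, exclusion criterion 13 and footnote h unchanged. Bullet 3's menses limb will then nearly repeat bullet 1, which does no harm.

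Go no further. A sentence reclassifying every woman whose periods stopped during anti-estrogen treatment would turn on timing and not on cause. Every patient has had such treatment, so it would also catch women who reached natural menopause while taking it and who meet bullet 1. An age cutoff would have no basis in the documents.

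The cost is two wording changes, a notice to sites, and IRB submission of the amendment under Section 14.1. A few women over 45 with drug-induced amenorrhea would move to the stricter standard or need an FSH and estradiol assay, which is not in the Schedule of Assessments. Where the cause of the amenorrhea is unclear, the investigator must judge it or use that assay. A newly reclassified woman whom the site had not regarded as pre/peri-menopausal would also need the baseline serum pregnancy test in exclusion criterion 13.

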Appendix D: Schedule of Assessments

Assessments	Baseline Study Assessments ^a	Study Treatment				Off-Treatment	Follow-Up	
		Cycles 1 and 2	Cycle 3	Cycle 4 +	Every 2 Cycles		Off Treatment Prior to Disease Progression ^l	Survival Follow-Up ^m
		Day 1	Day 1	Day 1		End of Study Treatment ^k		
Tests and Observations								
Informed consent	X							
Medical history	X	X	X	X		X	X	
Physical exam ^b	X	X	X	X		X	X	
ECOG PS	X	X	X	X		X	X	
ECG (single)	X							
Adverse event evaluation		X	X	X		X		
Concomitant medication review	X	X	X	X		X	X	
Study drug compliance assessment ^c		X	X	X		X		
Survival status								X
Laboratory Observations								
CBC, including 3-part differential, and platelets	X	X	X	X		X	X	
CMP ^d	X	X	X	X		X	X	
Fasting serum glucose	X	X	X	X		X		
Cholesterol/HDL/LDL/triglycerides ^{e,f}	X	X ^f	X	X ^f		X		
Hepatitis B and C screening	X ^o							
PT or INR, and PTT	X ^g							
Serum (or urine) pregnancy test ^h	X ^h		X ^h	X ^h		X ^h		
Urinalysis	X							
Archived tumor block	X ⁱ							
Serum sample for VeriStrat [®] assay	X ⁿ		X ⁿ			X ⁿ		X ⁿ
Staging								
CT scan of chest	X		X ^j		X ^j	X	X	
CT scan of abdomen and pelvis	X		X ^j		X ^j	X	X	
Bone scan	X ^j							

CONFIDENTIAL

SCRI INNOVATIONS STUDY NUMBER: BRE 212

VERSION 1.0

STUDY DRUG(S): EVEROLIMUS
FINAL PROTOCOL DATE: 19 JUNE 2014

Appendix D: Schedule of Assessments (continued)

- a The physical examination including neurological examination, update of medical history, ECOG PS, CBC, CMP plus uric acid, magnesium, phosphorus, and PT or INR, PTT must be done \leq 7 days prior to initiation of treatment. However, if these initial examinations are obtained within 72 hours of Cycle 1 Day 1 they do not have to be repeated. Scans to document measurable or evaluable disease (i.e., tumor measurement) must be performed \leq 4 weeks prior to initiation of treatment.
- b Physical examination will include measurements of height (to calculate body surface area [BSA]), weight, and vital signs (resting heart rate, blood pressure, respiratory rate, oral temperature) at the Pre-Treatment Visit. Physical examinations (PE) done at all other times during the study will include only measurements of vital signs and weight.
- c Study drug compliance will be assessed at each patient visit. The study staff will count and document the amount of study drug taken and returned by the patient.
- d CMP will include measurements of glucose, BUN, creatinine, sodium, potassium, chloride, calcium, CO₂, alkaline phosphatase, AST, ALT, total bilirubin, total protein, and albumin.
- e Patients must fast at least 8 hours overnight prior to collection of the blood specimen.
- f Cholesterol/HDL/LDL/triglycerides do not need to be repeated on Cycle 1 Day 1 if they are normal at baseline. Repeat on Day 1 of every odd cycle.
- g If PT or INR, and PTT are normal at baseline they do not need to be repeated. Patients requiring the initiation of an anti-coagulation therapy during study treatment should have their coagulation test performed as clinically indicated.
- h A serum pregnancy test for all pre/peri menopausal women (regardless of ovarian suppression) is required at baseline \leq 7 days prior to date of first treatment. All pre/peri menopausal women will need a serum or urine pregnancy test every 2 cycles (8 weeks) before receiving study treatment. If a urine pregnancy test is positive, it must be followed by a serum pregnancy test.
- i Tumor specimens from the primary site or from metastatic lesions will be collected from all patients with available archived tissue. See lab manual for details.
- j Scans are required every 2 cycles, prior to the start of odd-numbered cycles beginning with Cycle 3. Bone scans that are abnormal at baseline must be repeated at restaging.
- k After patients complete therapy or are discontinued from the study, they will visit the study center 30 days after finishing treatment for end-of-treatment assessments. CT scans performed within 8 weeks prior to the End of Treatment visit do not need to be repeated. All patients will be followed during the off study period until all treatment related toxicity resolves, and for at least 30 days post-study drug discontinuation.
- l Patients who discontinue study treatment prior to the occurrence of disease progression will be followed every 3 months (\pm 1 month) from the date of last dose of study drug until disease progression or for up to 3 years whichever comes first. A blood sample will be collected for the VeriStrat[®] assay at disease progression.
- m Patients will be followed for survival status after study treatment has ended (including the discontinuation of treatment for any reason prior to the end of the study) every 3 months (\pm 1 month) for up to 3 years or until patient death whichever comes first. A blood sample will be collected for the VeriStrat[®] assay at the 1st follow-up visit after disease progression. For subsequent follow-up visits, patients may be contacted during outpatient visits or by telephone.
- n Blood samples will be collected from all patients enrolled on the study for the VeriStrat[®] assay. Samples will be collected at baseline, prior to start of treatment on C3D1, at disease progression and at the 1st follow-up visit after disease progression.
- o HBV-DNA, HBsAg, HBcAb, HBsAb and/or HCV RNA testing applies only to patients at risk for hepatitis (Section 7.1)

CONFIDENTIAL

STUDY DRUG(S): EVEROLIMUS
FINAL PROTOCOL DATE: 19 JUNE 2014

SCRI INNOVATIONS STUDY NUMBER: BRE 212
VERSION 1.0

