7.3.4 Veri Strat® Assay Schedule

- Baseline visit (pre-treatment)
- Cycle 3 Day 1 visit (prior to treatment)
- At disease progression

CONFIDENTIAL

STUDY DRUG(S): EVEROLIMUS
FINAL PROTOCOL DATE: 19 JUNE 2014

SCRI INNOVATIONS STUDY NUMBER: BRE 212
VERSION 1.0

- At the first Follow-Up visit after disease progression

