7.5 End of Study Treatment

The follow-up evaluations required after treatment ends (due to disease progression, or once the patient is discontinued due to unacceptable toxicity or decision to discontinue treatment by the patient or the study physician) are specified in Appendix D. **A blood sample for the VeriStrat® assay will be collected from patients at the time of disease progression.**

After withdrawal from protocol treatment, patients must be followed for adverse events for 30 calendar days after the last dose of study drug. The following assessments will be performed for the End of Study Treatment Visit:

- Update of medical history
- PE including measurement of weight and vital signs
- ECOG PS (See Appendix A)
- AE assessment
- Concomitant medication review
- Study drug compliance assessment
- CBC, including 3-part differential and platelets
- CMP
- Fasting serum glucose
- Cholesterol, HDL, LDL, and triglycerides
- Serum or urine pregnancy test for all pre/peri menopausal women (regardless of ovarian suppression). If a urine pregnancy test is positive, it must be followed by a serum pregnancy test.
- CT scan of chest, abdomen and pelvis
- Blood sample for the VeriStrat® assay (only if patient is discontinued due to disease progression)

CONFIDENTIAL

STUDY DRUG(S): EVEROLIMUS
FINAL PROTOCOL DATE: 19 JUNE 2014

SCRI INNOVATIONS STUDY NUMBER: BRE 212
VERSION 1.0

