7.6 Follow-up

7.6.1 Follow-up for Patients Who Discontinue Prior to Disease Progression

Patients who discontinue study treatment prior to the occurrence of disease progression will be followed every 3 months (\pm 1 month) from the date of last dose of study drug until disease progression or for up to 3 years from the start of treatment whichever comes first. Assessments at these visits will be performed as described in Appendix D. **A VeriStrat serum sample will be collected from all patients at the time of disease progression.**

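### The protocol gives two conflicting times for the progression VeriStrat sample: at progression, or at a visit 30 days after treatment ends

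*Protocol*

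**What the plan says.** Several places in the protocol set the time of the sample by the event:

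- Section 7.3.4 lists "At disease progression" as a collection point, and Appendix G repeats it.
- The running text of Section 7.5 says "A blood sample for the VeriStrat® assay will be collected from patients at the time of disease progression".
- Section 7.6.1, for patients who stop treatment before progressing, says "A VeriStrat serum sample will be collected from all patients at the time of disease progression". Appendix D footnote l agrees.
- Appendix D footnote n, which is attached to the VeriStrat row of the grid, says "Samples will be collected at baseline, prior to start of treatment on C3D1, at disease progression and at the 1st follow-up visit after disease progression".

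Other places set it by the visit:

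- The Section 7.5 checklist for the End of Study Treatment visit includes the VeriStrat draw, "only if patient is discontinued due to disease progression".
- The Appendix D grid marks VeriStrat serum in four columns: Baseline, Cycle 3, End of Study Treatment and Survival Follow-Up. The Cycle 4+, Every 2 Cycles and Off Treatment Prior to Disease Progression columns are blank.
- Footnote k dates the End of Study Treatment visit: patients who complete or stop therapy are told that "they will visit the study center 30 days after finishing treatment for end-of-treatment assessments".
- Sections 7.3.3 (Cycle 4 and later) and 7.4 (restaging) list no VeriStrat draw. Section 7.3.2 does, but that is the scheduled Cycle 3 Day 1 sample.

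**The concern.** Scans are done every two cycles, so progression on treatment will mostly be found at restaging. At that visit the schedule does not tell the site to draw serum. The visit that does carry the instruction comes about a month after treatment stops. Two sites could each follow the protocol and supply different specimens under the same name, one taken at progression and one taken about 30 days off everolimus.

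Section 5.4 bars other systemic anticancer agents only until RECIST progression is documented. A patient sampled at the 30-day visit may therefore already be receiving another drug. If both kinds of specimen are pooled as the progression sample, a difference from baseline or Cycle 3 could reflect everolimus withdrawal or a new therapy, and the data would not separate these. A draw that was missed at progression cannot be recovered later.

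**Working it through.** The plan states no figure on this point, so the check is mainly a comparison of the passages.

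**Step 1: which visit carries the draw for a patient who progresses on treatment?**

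| Place | Instruction | Implied time |
|---|---|---|
| 7.3.4; 7.5 text; footnote n; Appendix G | Draw at progression | Day progression is documented |
| 7.3.3; 7.4; grid columns Cycle 4+ and Every 2 Cycles | No draw listed | None |
| 7.5 checklist; grid column End of Study Treatment | Draw at this visit if stopped for progression | Set by footnote k |
| Footnote k | Visit 30 days after finishing treatment | About day 30 off treatment |

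The only visit that carries the draw is the one dated by footnote k. Footnote k also excuses CT scans done within the previous 8 weeks, so it treats this visit as separate from the one at which the progression scan was obtained.

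**Step 2: how far apart are the two readings?** Progression is a reason for stopping treatment (Section 3.3). Assuming treatment stops when progression is documented, the gap is about 30 days. The patient is then off everolimus, with no further assumption needed.

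**Step 3: patients who stop before progression.** They are followed every 3 months (± 1 month) and are already off everolimus when they progress, so footnote k does not affect their sample. Footnote l requires a draw at progression, but their grid column has no VeriStrat mark.

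**Step 4: would the patient be on a new therapy by day 30?** The documents give no time to next therapy. As an illustration only, assume an exponential time with median m days, so that the share started by day 30 is 1 − 2^(−30/m):

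| Assumed median m | Share started by day 30 |
|---|---|
| 14 days | 77% |
| 21 days | 63% |
| 28 days | 52% |
| 42 days | 39% |
| 56 days | 31% |

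The answer depends almost wholly on m. It also applies only to samples actually drawn at the 30-day visit.

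**Step 5: could late samples be identified afterwards?** The Appendix G labels already carry visit type and collection date. SAP Listing 3 (the Biodesix listing) holds treatment start, best response and its date, PFS and OS. It has no draw date, last-dose date or start of subsequent therapy.

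**The case against.** The best reply is that the specific instruction governs the general one. Footnote n deals with this sample alone and is attached to the End of Study Treatment cell itself; it says "at disease progression and at the 1st follow-up visit after disease progression". Footnote k is a general note on the visit, and Section 7.5 gives no day for that visit. A site reading this way would sample on time. This stands to the extent that day 30 is not a settled assignment, and a reader should not infer that every patient who progresses on treatment would be sampled a month late. It does not remove the conflict, because the protocol never says that footnote n prevails and no visit list puts the draw where progression is found.

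Three further inferences are tempting, and the documents do not support them.

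- **That these samples would often be drawn on next-line therapy.** Section 5.4 permits it, but no timing is given and the illustrative range is wide.
- **That a planned result is harmed, such as a profile of serum at resistance.** The objective is only to evaluate the assay. Appendix G describes a pre-treatment test, counts only baseline samples (about 4 VeriStrat Poor expected among 46) and leaves the feasibility of any analysis open. The SAP specifies no analysis of the progression sample.
- **That a 30-day draw merely duplicates the first follow-up sample.** Follow-up is every 3 months ± 1 month, so that sample would usually come well after day 30. It is true only that both would be off treatment.

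It is also fair to say that the collection date is already recorded on the label. That helps to identify late samples, but it does not replace a sample that was not drawn at progression.

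**Conclusion.** The point holds as an unreconciled contradiction about when one exploratory sample is taken. For patients who stop because of progression, the two readings differ by about 30 days, assuming treatment stops when progression is documented. On the later reading the patient is off everolimus and may have started another therapy; how often cannot be derived from the documents. How many sites would follow each reading is also unknown.

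The consequence is minor. Only the exploratory VeriStrat objective is touched. PFS, the sample size, safety, and the baseline and Cycle 3 Day 1 samples are unaffected. It is still worth correcting before enrolment, because the change is small and mixed sample timing cannot be repaired once the draws are made.

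**What to change.** 1. Reconcile Sections 7.4 and 7.5, the Appendix D grid and footnotes k and n. Tie the progression draw to the visit at which RECIST progression is documented, state a collection window, and remove the draw from the 30-day visit. The window matters because the scan result may not be known on the day of the scan. The draw should not delay any treatment.
2. Mark the draw in the Off Treatment Prior to Disease Progression column, as footnote l already requires.
3. Add three dates to the VeriStrat dataset (SAP Listing 3): collection date from the label, last dose of study treatment, and start of subsequent therapy. Samples drawn after a new therapy began can then be identified and set apart.

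The cost is a small change to schedule wording, three added fields in a listing, and one more draw for sites to coordinate around restaging. The number of samples and kits does not change.
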